# Criteria for Selection of Subjects

Inclusion: Pregnant people, 18 years of age or older; intrauterine pregnancy between 18/0-23/6 weeks of gestational age (by ultrasound dating performed prior to same day of enrollment visit) consented for an induced abortion; English or Spanish speaking, able to consent for a research study, literate in English or Spanish.

Exclusion: known coagulopathy, suspected morbidly adherent placenta spectrum, multiple gestation, current infection, ruptured membranes, or fetal demise at time of enrollment.

# Subject Recruitment and Allocation

Subjects will be recruited from Stanford Gynecology Clinic on the day of their Family Planning consultation, after consent for, but prior to abortion. Only patients in the appropriate gestational ages will be approached. Potential participants will be screened for the study and if eligible and willing to participate in the project they will be consented for the study.

# Description of Drugs and Devices

Misoprostol is a prostaglandin E1 analogue with two FDA labeled indications: 1. prevention of nonsteroidal anti-inflammatory drug-induced gastric ulcers and 2. Termination of intrauterine pregnancy through 70d gestation in combination with mifepristone. Various off label uses exist in obstetric, gynecologic, and abortion care including cervical preparation and labor induction, early pregnancy loss, incomplete abortion, postpartum hemorrhage (prevention/treatment), termination of intrauterine pregnancy as monotherapy.

#### Data Management & Analysis

Stanford University has a license for the RedCap data management system(Harris et al., 2009). RedCap is a web-based application that is secure, reliable, and HIPAA-compliant for strong research study data. RedCap is designed with build-in features to address confidentiality and compliance requirements. Electronic surveys will be administered via study iPad on the day of the procedure. Data associated with patient health identifiers (PHI) including the signed informed consent will be collected electronically. RedCap allows for easy data download into SAS or other statistical software programs. No data will be collected on paper forms. SAD OnDemand will be used for data analysis. Data will be analyzed with parametric or non-parametric statistical tests, as appropriate.

Misoprostol Effect on Second Trimester Abortion Blood Loss

Statistical Analysis Plan

NCT06078501

August 23, 2023

To detect a 30% reduction in the proportion of participants with quantitative blood loss (QBL) greater than the median, with a two-sided alpha of 0.05 and 80% power, we calculated that 36 participants per group would be needed. To allow for attrition, we planned to recruit 40 participants per group, for a total of 80 participants.

Descriptive statistics will be used to summarize baseline characteristics. Continuous variables will be compared using t-tests or Wilcoxon rank-sum tests, depending on distribution. Categorical variables will be compared using chi-square or Fisher's exact tests. Multivariable logistic regression was used to estimate the association between treatment group and the primary outcome (QBL greater than the median), adjusting for potential confounders.

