### Non-technical summary:

Although serious complications from second trimester abortion are rare hemorrhage is the most common cause of procedural abortion related morbidity and mortality (Zane et al., 2015). Misoprostol is a prostaglandin E1 analogue that is used by 75% of clinicians (White et al., 2018) prior to procedural abortion for the purpose of cervical preparation. Misoprostol is also known to decrease blood loss in first trimester abortion and is used to treat postpartum hemorrhage, however the effect of preprocedural misoprostol on second trimester abortion blood loss is not well described.

We will conduct a double blinded placebo-controlled gestational age stratified superiority trial of those undergoing procedural abortion between 18 and 23 weeks gestation at Stanford Health care. Participants will be randomized to either 400mcg buccal misoprostol or placebo on the day of the procedure. A quantified blood loss (QBL) will be measured during the procedure and participants will complete a survey to assess symptoms. Our primary outcome is quantified blood loss. Secondary outcomes include clinical interventions to manage excess bleeding, total procedure time, provider reported experience, patient reported experience. We plan to recruit 80 subjects powered to detect a 30% reduction in QBL in those who received misoprostol compared to the control group.

This study has the potential to increase the safety of an already safe procedure and establish clinical benefits of choosing misoprostol as an agent for cervical preparation.

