# Secondary aims:

Patient experience: evaluate the subjective experiences of patients who receive misoprostol before second trimester abortion focusing on pain before and after administration of the treatment, side effects, and overall satisfaction with the experience.

Procedure: analyze whether the use of misoprostol prior to second trimester abortion influences the procedure times, ease of procedure, provider estimated blood loss, provider satisfaction with cervical preparation, and whether the clinician could tell whether misoprostol was used.

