#### Research Design and General Methodological Approach

The proposed study is a conduct a randomized, double-blinded, placebo-controlled, superiority trial. Participants will be consented and randomized using a computer-generated random number producing algorithm to receive either misoprostol 400mcg or placebo, buccally 90-120 minutes prior to their scheduled procedure time. Pharmacy staff filled identical, opaque pill containers with either two 200mcg misoprostol tablets or two 50-mg vitamin B6 tablets (placebo) because no identical appearing placebo exists for misoprostol. To ensure blinding of research and clinical staff subjects will self-administer study tablets in private where a research assistant who is uninvolved with collection of data will be available to assist patients with correct buccal placement. All other clinical and research staff will be blinded to the study group assignments until data analysis is complete.

The primary outcome will be proportion of participants with blood loss (QBL) above published medians by gestational duration(Serapio et al., 2018). To detect a 30% reduction in the proportion of participants with QBL greater than the median, with an alpha of 0.05 and a power of 80%, we would need 36 participants per group. Accounting for drop out, loss to follow up, and missing data, we plan to recruit 40 per group, for a total of 80 participants. With an estimated 180 procedures per year, 80% eligible, and 60% enrollment, we estimate the study will take 12-15 months to enroll. QBL will be measured using previously published protocols(Serapio et al., 2018). QBL was selected as the primary outcome because the incidence

of hemorrhage in second trimester abortion is a rare outcome. Lower QBLs correspond to lower risks and rates of hemorrhage therefore QBL may be a reasonable proxy to understanding morbidity and mortality related to procedural second trimester abortion.

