Secondary outcomes will include clinical intervention to manage excess bleeding (use of uterotonics, uterine artery embolization, uterine balloon tamponade, blood transfusion, hysterectomy), total procedure time, provider-reported experience (ease of procedure, provider estimated blood loss, provider satisfaction with cervical dilation, and whether the clinician accurately predicted which treatment arm the subject was in), participant-reported experience (pain, side effects: nausea, vomiting, diarrhea, fevers), preoperative exam for dilation, need for mechanical dilation. Patient and provider experience are important outcomes to consider as some providers specifically chose methods of cervical preparation based on patient experiences and based on the way that the provider themselves perform the procedure. Because there is no one standard way to prepare cervices for second trimester procedural abortion providers choose methods of cervical preparation that they are most comfortable and familiar with based on how it changes the way they perform the procedure itself and how patients tolerate the various methods of cervical preparation. For example, pharmacologic preparation with misoprostol may cause side effects such as nausea, diarrhea, and fever, whereas osmotic dilators may cause more pain with placement and more pain overnight prior to procedure.

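### Pain before and after study drug is a secondary aim, but the SAP states no use of the pre-dose score; prespecified baseline adjustment could add modest precision at almost no cost

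*SAP*

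**What the plan says.** The protocol's Secondary aims section describes the patient-experience aim as "focusing on pain before and after administration of the treatment, side effects, and overall satisfaction with the experience". The secondary-outcomes paragraph under Research Design and General Methodological Approach lists pain among participant-reported outcomes, with no scale and no assessment time.

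On analysis, the SAP states that "Continuous variables will be compared using t-tests or Wilcoxon rank-sum tests, depending on distribution". The sentence just before it is "Descriptive statistics will be used to summarize baseline characteristics". The SAP's only regression model is a logistic model for the primary outcome, with covariates it does not name. The protocol's Data Management & Analysis section adds only that "Data will be analyzed with parametric or non-parametric statistical tests, as appropriate".

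Neither document says whether the pre-dose pain score is to be a covariate, subtracted to form a change score, or merely described.

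**The concern.** A before-and-after assessment supplies a baseline value of the outcome itself, often a useful covariate. The SAP text leaves at least two unadjusted analyses open. A test on post-dose scores ignores the baseline. A test on change scores gives it a fixed weight of 1. Regression of post-dose pain on treatment and pre-dose pain estimates that weight from the data.

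Two things are at stake. One is the width of the confidence interval for the pain difference. The other is the freedom to choose between post-dose and change scores once data are in hand, because the two can differ noticeably in power. The pain result matters to the trial's purpose: the protocol notes that "some providers specifically chose methods of cervical preparation based on patient experiences". The primary outcome, the sample size and the type I error of the primary test are not affected.

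**Working it through.** **Inputs from the documents.** Two-sided alpha 0.05, 80% power, 36 evaluable per group and 40 recruited per group (SAP).

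**Assumed, because the documents give no value.** Before-after correlation r from 0 to 0.7, normal scores, equal SDs in both arms and at both times. Differences are in SD units.

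**The plan's own figure.** Reading the target as 50% versus 20% above the median (an absolute reduction of 30 points, which is an assumption), with unpooled variance:

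(1.960 + 0.842)² × (0.50×0.50 + 0.20×0.80) / 0.30² = 35.76, so 36 per group; 36 / 0.90 = 40.

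The stated size reproduces. It concerns blood loss only; the trial was not sized for pain. I use N = 72 below.

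**Variance of the treatment difference, relative to the post-score comparison**

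- Post score: 1
- Change score: 2(1 − r)
- Baseline-adjusted: (1 − r²) × (N − 3)/(N − 4) = (1 − r²) × 69/68 = (1 − r²) × 1.0147

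The last factor is the cost of estimating the slope.

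**Break-even points**

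- Against post scores, adjustment wins when r > √(1/69) = 0.120. With all 80 evaluable it is √(1/77) = 0.114. A simulation of 100,000 trials at N = 72 and r = 0.12 gave a variance ratio of 1.000.
- Against change scores, adjustment wins when 1 + r < 2/1.0147, that is r < 0.97.
- At r = 0 adjustment costs 1.5% in variance, or 0.7% in standard error.

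**Difference detectable with 80% power, 36 per group.** The normal approximation for post scores gives 2.802 × √(2/36) = 0.66 SD. Using the t distribution raises this to 0.67 SD. The other entries are 0.67 times the square root of the relative variance.

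| r | Post | Change | Adjusted |
|---|---|---|---|
| 0.3 | 0.67 | 0.67×√1.4 = 0.79 | 0.67×√0.923 = 0.64 |
| 0.5 | 0.67 | 0.67×√1.0 = 0.67 | 0.67×√0.761 = 0.58 |
| 0.7 | 0.67 | 0.67×√0.6 = 0.52 | 0.67×√0.517 = 0.48 |

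**Power at a true difference of 0.66 SD (noncentral t)**

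| r | Post | Change | Adjusted | Gain over better unadjusted test |
|---|---|---|---|---|
| 0.1 | 78.9% | 53.9% | 78.7% | about 0 |
| 0.3 | 78.9% | 64.6% | 81.9% | about 3 |
| 0.5 | 78.9% | 78.9% | 88.6% | about 10 |
| 0.7 | 78.9% | 94.6% | 97.0% | about 2 |

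Simulation with 40,000 runs agreed to within about one point, and null rejection was 4.8 to 5.0% for all three methods. Against the better unadjusted option, the 95% CI is about 0, 4, 13 and 7% narrower.

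**Sensitivity to zeros (assumed 0–10 integer scale, Wilcoxon as the unadjusted test), r = 0.1, 0.3, 0.5, 0.7**

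- About 16% zeros post-dose on placebo: gains 1.5, 3.9, 8.3 and 2.0 points.
- About 73% zeros pre-dose and 42% post-dose on placebo: about 1, 3, 2 and 2 points.
- About 84% and 58%: about −1, 0, 1 and 1 points.

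Simulation error in the last two is about 1 point. With mostly zero pre-dose scores, the gain is therefore roughly 0 to 2 points.

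**The case against.** The strongest reply is that no error has been shown. The unadjusted tests are valid under randomisation, the protocol allows whatever test is appropriate, and the SAP does not exclude adjustment for secondary outcomes. A reader might infer from the silence on pre-dose pain that the planned comparison is biased, or that adjustment is ruled out. The documents support neither: chance baseline differences between arms cost precision, not validity, and naming a model for the primary outcome does not forbid one elsewhere. That part of the reply stands in full.

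Second, the quoted SAP sentence may not govern pain at all. It follows a sentence on baseline characteristics and may cover only baseline comparisons, and with no scale given, pain may not be a continuous variable. This also stands, but it does not close the gap. On that reading pain has no named method beyond the protocol's general statement, and the same SAP paragraph is needed.

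Third, the threshold of 0.12 applies only against a post-score test. A reader might infer that any correlation above it brings a worthwhile gain. It does not: the gain is zero at the threshold and about 3 power points at r = 0.3. Against a change-score test the condition is different, and adjustment wins at almost any r.

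Fourth, every magnitude is assumed, and heavy zeros can nearly remove the gain. This is correct and limits the point to an optional improvement. What survives is that adjustment was at or within about 1 point of the better unadjusted test in every scenario examined, so the sponsor need not guess r in advance.

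**Conclusion.** The point holds as a minor improvement, not a defect in validity. The plan calls for pain before and after study drug and states no use of the earlier score. Under normal scores with 36 per group, adjustment lowers the detectable difference from 0.67 SD on post scores to 0.64, 0.58 or 0.48 SD at r = 0.3, 0.5 or 0.7. Only r near 0.5 gives a notable gain over the better unadjusted test.

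The choice between the two unadjusted tests matters more than these gains suggest. A change-score test loses about 25 power points to the post-score test at r = 0.1 (78.9 − 53.9) and 14 at r = 0.3 (78.9 − 64.6). The post-score test loses about 16 to the change-score test at r = 0.7 (94.6 − 78.9). Fixing one analysis beforehand removes that uncertainty.

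The conclusion that the SAP is silent rests on its text. The size of the benefit rests wholly on assumed correlation, distribution and effect.

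**What to change.** Add one paragraph to the SAP: pain at one named post-dose time point will be compared between arms by linear regression on treatment and pre-dose pain, and the adjusted mean difference with its 95% CI will be reported. State the pain scale and both assessment times.

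If the scale is ordinal with few levels, or many zeros are expected, prespecify instead a proportional-odds model with the same covariate. Make that choice from the scale and the expected distribution, not from the trial data. Keep the t-test or Wilcoxon test for continuous outcomes that have no baseline value.

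The cost is one SAP paragraph and one degree of freedom. No extra participants are needed, and no extra data if the planned pain assessments are carried out.

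Whether randomisation is stratified is a separate issue. The protocol summary describes a "double blinded placebo-controlled gestational age stratified superiority trial", while the methods section says participants are "consented and randomized using a computer-generated random number producing algorithm" and mentions no strata. Reconcile the two before deciding whether gestational age belongs in this model.

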#### **Specific Aims:**

Primary aim:

To investigate the impact of administering 400 micrograms of buccal misoprostol 90-120 minutes prior to second trimester procedural abortion on quantified blood loss.

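### The protocol summary says 80 participants give power for a 30% reduction in QBL, but the sample size was calculated for a 30-point drop in the proportion above a median, and QBL in mL has no named analysis

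*SAP*

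**What the plan says.** The Non-technical summary of the protocol states "Our primary outcome is quantified blood loss", with no cut-point, and describes the 80 participants as "powered to detect a 30% reduction in QBL in those who received misoprostol compared to the control group". The primary aim (Specific Aims) concerns the effect of misoprostol "prior to second trimester procedural abortion on quantified blood loss".

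The section Research Design and General Methodological Approach is more specific: "The primary outcome will be proportion of participants with blood loss (QBL) above published medians by gestational duration". Its sample size rests on that proportion: "To detect a 30% reduction in the proportion of participants with QBL greater than the median", with alpha 0.05 and 80% power, giving 36 per group and 40 after attrition. It does not say whether the 30% is absolute or relative, and it gives no control-group proportion. Further on, the same section again refers to QBL itself as the chosen primary outcome.

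The SAP repeats the 36 and 40 per group, adds that alpha is two-sided, and refers only to the median, without saying that it is published or gestation-specific. Its one analysis tied to the primary outcome is binary: "Multivariable logistic regression was used to estimate the association between treatment group and the primary outcome (QBL greater than the median". It also has a general rule that continuous variables are compared by t-test or Wilcoxon rank-sum test. The protocol's Data Management & Analysis section has a similar general sentence. Neither mentions QBL.

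**The concern.** A 30% reduction in blood loss and a 30% reduction in the proportion above a median are different effects, and a sample size for one does not carry over to the other. Someone who reads the summary would take a null result as reasonable evidence against a 30% reduction in volume, because the trial is said to have adequate power for it. That inference is safe only if the power statement is true for volume.

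The planned primary result is an odds ratio for exceeding a median. It does not say by how many mL, or by what percentage, misoprostol changes blood loss. No document commits the trial to an estimate of that quantity with a confidence interval.

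**Working it through.** **Inputs from the documents:** two-sided alpha 0.05, 80% power, 36 per group, 40 after attrition. The Background and Significance section gives interquartile ranges from a cited oxytocin trial: 168-464 mL (control) and 98-235 mL (oxytocin).

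**Assumed:** a control proportion of 50%, inferred from the word median; the control median equal to the published median; log-normal QBL with the same log-scale spread in both groups. The documents give no SD for QBL in this trial.

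**1. Reproduce the 36.** With unpooled variance, n = (1.960 + 0.842)² × [p1(1−p1) + p2(1−p2)] / (p1−p2)², where (1.960 + 0.842)² = 7.849.
- 50% vs 20%: 7.849 × (0.25 + 0.16) / 0.09 = 35.8, so 36. The pooled-variance form gives 38.5.
- 50% vs 35%: 7.849 × (0.25 + 0.2275) / 0.0225 = 166.6. The pooled form gives 169.3.

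The stated figure therefore fits 30 percentage points absolute and not a relative 30%. For attrition, 36 / 0.90 = 40.

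**2. Power of the binary comparison** (chi-square test, exact binomial calculation):

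| Above median, control vs misoprostol | 36 per group | 40 per group |
|---|---|---|
| 50% vs 20% | 79% | 82% |
| 50% vs 35% | 24% | 29% |

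**3. What a 30% lower QBL does to the proportion.** Log-SD = ln(Q3/Q1) / 1.349.
- Control arm of the cited trial: ln(464/168) / 1.349 = 0.75.
- Oxytocin arm: ln(235/98) / 1.349 = 0.65.

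The share of treated participants above the control median is Φ(ln 0.7 / log-SD), with ln 0.7 = −0.357.
- Log-SD 0.65: Φ(−0.549) = 29%.
- Log-SD 0.75: Φ(−0.476) = 32%.

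**4. Power for a 30% lower QBL** (rank-test figures by simulation, 20,000 trials per cell):

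| Log-SD | Test | 36 per group | 40 per group |
|---|---|---|---|
| 0.65 | Median split | 44% | 49% |
| 0.75 | Median split | 35% | 40% |
| 0.65 | Wilcoxon | 61% | 65% |
| 0.75 | Wilcoxon | 49% | 54% |

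**5. When would the two statements agree?** A 30% lower QBL gives 50% vs 20% only if log-SD = 0.357 / 0.8416 = 0.42. In the other direction, reaching 20% above the median needs QBL lower by 1 − exp(−0.8416 × log-SD), which is 42% at log-SD 0.65 and 47% at 0.75.

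**The case against.** The conflict sits mainly in a lay summary. The methods section and the SAP agree on a binary outcome, on 36 and 40 per group, and on alpha and power. The authors also seem to use QBL as shorthand: the methods section defines the binary outcome and then calls it QBL. This stands. It makes the sizing itself sound and the repair small, but the summary still makes a power claim that the calculation does not support.

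The primary aim need not conflict with anything. A threshold on QBL is one way to study an effect on blood loss, so the aim does not require a continuous primary.

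A reader might infer that the plan allows no comparison in mL. The documents do not support that. The SAP's t-test or Wilcoxon rule would by default cover a measured volume, although it follows the sentence on baseline characteristics. What is missing is any mention of QBL in mL as an endpoint, with its own estimate and interval.

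A reader might also infer that the trial is shown to be underpowered. That goes too far. The power figures for volume use spreads from another trial, pooled over gestational duration, while this trial's cut-point is gestation-specific. A smaller spread would raise power. Under the log-normal assumption, gestational age would have to explain about 57-68% of the variance of log QBL to bring log-SD down to 0.42 (1 − (0.424/0.648)² = 0.57; 1 − (0.424/0.753)² = 0.68). The documents neither show nor exclude this.

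Finally, a reader might infer that continuous QBL must become the primary outcome. It need not. The gain from a rank test at 50% vs 20% depends on the shape of the distribution: from essentially none under a truncated normal to 92-93% against 79% power under a log-normal. The two arms of the cited trial suggest different shapes. The oxytocin arm is almost exactly log-symmetric (152/98 = 1.55, 235/152 = 1.55), while the control arm is not (317/168 = 1.89, 464/317 = 1.46).

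**Conclusion.** The concern holds in this form. The summary's statement of power for a 30% reduction in QBL does not describe the calculation that was done, and no calculation or SD in the documents supports it. The 36 per group reproduces for 50% vs 20% above the median, given the inferred 50% control rate; the binary design then has about 79% power at 36 and 82% at 40 per group. If a relative 30% was meant, power is only about 24-29%.

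For a 30% lower QBL, power at 36-40 per group is about 35-49% with the planned median split and about 49-65% with a rank test, under log-normal spreads borrowed from another trial. These ranges are illustrations, not estimates for this trial. That the two 30% statements are different targets does not depend on them: they coincide for the binary test only at a log-SD of about 0.42. The missing named analysis in mL is a gap in specification and does not invalidate the primary analysis.

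**What to change.** 1. In the Non-technical summary, replace the power statement with the target that was sized. There, in the methods section and in the SAP, state the effect as 50% vs 20% above the published gestation-specific median (30 percentage points absolute), if that was intended, with about 79% power at 36 and 82% at 40 per group. If a relative 30% was intended, say so and report power of about 24-29%. Use one wording for the primary outcome in all three places.

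2. Keep the binary primary and add one named supporting analysis of QBL in mL: a Wilcoxon test that accounts for gestational age, with the Hodges-Lehmann difference in mL, the geometric mean ratio, or both, each with a 95% CI. Write down the gestational-age categories used. The summary describes a "double blinded placebo-controlled gestational age stratified superiority trial", but the methods sentence says only that participants are "randomized using a computer-generated random number producing algorithm", and no strata are given.

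**Cost:** no new participants or data, some rewording and one extra analysis. The power statement for a 30% lower QBL becomes less favourable. Making continuous QBL the primary is optional and legitimate only before unblinding; the SAP is partly in the past tense, so the documents do not show whether that is still possible. This point does not require it.
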